### 10.1. Exposure

#### 10.1.1. Extent of Exposure

The summary of *i*) planned and actual RC-P administration status by course, and *ii*) the descriptive summary of planned and actual number of courses of RC-P will be provided. Study drug administration details such as the course number, actual dose, start and end day/time of the study drug administration will be listed separately.

#### 10.1.2. Treatment Compliance

Not applicable for this study since RC-P administration will vary depending on the number of doses of a long-acting *E. coli*-derived asparaginase remaining on an individual patient's original treatment protocol.

### 10.2. Adverse Events

AEs recorded in the case report form will be coded to system organ class (SOC) and preferred term (PT) using the Medical Dictionary for Regulatory Activities (MedDRA 22.1). The investigator will assess the relatedness of each AE to study drug. The severity of AEs will be recorded using the Common Terminology Criteria for Adverse Events (CTCAE 5.0).

At a minimum, the investigator must record all AEs that occur from the time written informed consent is obtained until screen failure if applicable, or 30 days after the patient's last dose of the last course of RC-P, regardless of their relationship to study drug. Any serious AE (SAE) assessed as related to study drug by the investigator that occurs more than 30 days after the patient's last dose of the last course of RC-P should be reported regardless of time after study termination.

A treatment-emergent adverse event (TEAE) is defined as any event with onset date on or after Study Day 1 through the end of the study or any ongoing event that worsens in severity after Study Day 1 through the end of the study. Only TEAEs with the onset date through the end of the AE reporting period will be included in summary tables unless otherwise specified. For the purpose of calculating treatment emergence, incomplete onset dates will be imputed as detailed in [Appendix I](#).

AEs are graded by the investigator as Grade 1 (mild), Grade 2 (moderate), Grade 3 (severe or medically significant but not immediately life-threatening), Grade 4 (life-threatening consequences), or Grade 5 (Death related to AE). The severity grade of events for which the investigator did not record severity will be categorized as "missing" for tabular summaries and data listings, and will be considered the least severe for the purposes of sorting for data presentation.

Treatment-related AEs are those for which the investigator answers "Yes" to the question "Was this adverse event related to study treatment?" in the eCRF. Events for which the investigator did not record relationship to study treatment will be considered related to study treatment for summary purpose. Data listings will show treatment-relationship as missing. AEs for which "Yes"

Jazz Pharmaceuticals Ireland Limited  
Statistical Analysis Plan – Protocol JZP458-201

is marked for question “Was this adverse event related to study procedure?” in eCRF will be identified and included in AE listing.

SAEs are those for which the investigator answers “Yes” to the question “Was the adverse event serious?” in the eCRF. The clinical database will be reconciled with the SAE database before database finalization.

For all AE summaries, if a patient has more than 1 AE within a PT, the patient is counted only once at the maximum severity and with the closest relationship to study drug. If a patient has more than 1 AE within a SOC, the patient is similarly counted once when reporting results for that SOC.

A brief summary of TEAEs (i.e., the number and percentage of patients) will be presented by dose level of RC-P, and route of administration (IM or IV) for the following: (1) any TEAE, (2) any serious TEAE, (3) any treatment-related TEAE, (4) any serious treatment-related TEAE, (5) any Grade 3 or 4 TEAE, (6) any treatment-related Grade 3 or 4 TEAE, (7) any TEAE leading to study drug discontinuation, (8) any treatment-related TEAE leading to study drug discontinuation, (9) any TEAE leading to death, and (10) any treatment-related TEAE leading to death.

A general summary of TEAEs by SOC and PT will be provided with the number and percent of patients who experienced the following types of events by dose level of RC-P, and route of administration (IM or IV). For data presentation, SOC will be ordered alphabetically, with PT sorted by decreasing frequency in the final dose of IM:

- Patients with any TEAE
- Patients with any serious TEAE
- Patients with any treatment-related TEAE
- Patients with any serious treatment-related TEAE
- Patients with any Grade 3 or 4 TEAE
- Patients with any treatment-related Grade 3 or 4 TEAE
- Patients with any TEAE leading to study drug discontinuation
- Patients with any treatment-related TEAE leading to study drug discontinuation
- Patients with any TEAE leading to death
- Patients with any treatment-related TEAE leading to death

Data listings will be provided for the following including patient number, dose level of RC-P, route of administration (IM or IV), SOC, PT, date of onset/stop, severity, seriousness, treatment-relationship, action taken:

- All AEs
- Serious AEs
- Treatment-related AEs
- Serious treatment-related AEs
- Grade 3 and 4 AEs

Jazz Pharmaceuticals Ireland Limited  
Statistical Analysis Plan – Protocol JZP458-201

- AEs leading to study drug discontinuation
- Death report

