6.2. Demographics/Medical History

Demographic information will be collected and recorded at Screening as permitted by regional or national regulations and should include the date that the patient (or guardian as applicable) signed the ICF, patient's age (as indicated by date of birth), sex, ethnicity, and race.

A complete medical history will be taken during Screening and should be reviewed for completeness prior to enrollment. Medical History review is required to ensure the patient is still eligible for enrollment and should ensure that all medical conditions, surgeries or procedures that occurred before the patient signed ICF are documented. Conditions that occur after the patient has signed ICF will be recorded as AEs (Section 6.7.6).

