6.7.6.2. Severity Assessment

Adverse events will be classified by the Investigator using the National Cancer Institute (NCI) Common Terminology Criteria for Adverse Events (CTCAE), version 5.0. All appropriate treatment areas should have access to a copy of the CTCAE version 5.0. A copy of the CTCAE version 5.0 can be downloaded from the Cancer Therapy Evaluation Program website (<http://ctep.cancer.gov>). If the CTCAE grade is not specified for a particular event or if the event term does not appear in the CTCAE, general guidelines for grading severity of AEs are provided in [Table 5](#). When the severity of an AE increases over time, the increase in the severity will be recorded as a new AE and the original AE will stop when the new AE starts except in the following scenario.

Cohort 1 (Part A and Part B): From the time written informed consent is obtained through completion of Course 1, when the severity of an AE changes over time, the decreases and increases in severity will be recorded as a new AE, and the original AE will stop when the new AE starts.

The CTCAE should be used for severity assessment only; it is not intended for use in event term selection (see [Section 6.7.6.1](#) for AE terminology).

Table 5: CTCAE Severity Grades General Guidelines v5.0

Grade 1	Mild; asymptomatic or mild symptoms; clinical or diagnostic observations only; intervention not indicated.
Grade 2	Moderate; minimal, local or noninvasive intervention indicated; limiting age-appropriate instrumental activities of daily living (ADL) ^a .
Grade 3	Severe or medically significant but not immediately life-threatening; hospitalization or prolongation of hospitalization indicated; disabling; limiting self-care ADL ^b .
Grade 4	Life-threatening consequences; urgent intervention indicated.
Grade 5	Death related to AE.

^a Instrumental ADL refers to preparing meals, shopping for groceries or clothes, using the telephone, managing money, etc.

^b Self-care ADL refers to bathing, dressing and undressing, feeding self, using the toilet, taking medications, and not bedridden.

Note: A semi-colon indicates 'or' within the description of the grade.

Abbreviations: ADL=activities of daily living; AE=adverse event; CTCAE=Common Terminology Criteria for Adverse Events.

Source: CTCAE v5.0 accessed at:

https://ctep.cancer.gov/protocolDevelopment/electronic_applications/docs/CTCAE_v5_Quick_Reference_8.5x11.pdf

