6.7.6.6. Follow-up of Adverse Events

All AEs and SAEs assessed as not related to study drug, including clinically significant laboratory tests, or physical examination findings, must be followed until the event resolves, the condition stabilizes, the event is otherwise explained, or the final study visit occurs, whichever comes first.

Adverse events and SAEs assessed as related to study drug, and AEs and SAEs resulting in discontinuation of study drug or study termination should be followed for as long as necessary to adequately evaluate the patient's safety, or until the event stabilizes, or the patient is lost to follow up. If the event resolves during the study, a resolution date should be recorded, for both AEs and SAEs. If at the time of the final scheduled study visit, the AE is not resolved, the

outcome at that time should be recorded. Once the final outcome is determined for an SAE this information should be provided as follow-up SAE information.

The Investigator is responsible for ensuring that follow-up includes any supplemental investigations indicated to elucidate the nature and/or causality of the event. This may include additional clinical laboratory testing or investigations, examinations, histopathological examinations, or consultation with other health care professionals as is practical, according to Jazz Pharmaceuticals' requests.

The Investigator should provide follow-up SAE information for any updates to information previously provided to Jazz Pharmaceuticals.

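### Does the TEAE definition count improving pre-dose adverse events in Cohort 1 but not in Cohort 2?

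*SAP*

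**What the plan says.** SAP 10.2 gives the TEAE definition two limbs. A TEAE "is defined as any event with onset date on or after Study Day 1" or is "any ongoing event that worsens in severity after Study Day 1 through the end of the study". Study Day 1 is the date of the first RC-P dose (SAP 7.2.1).

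Protocol 6.7.6.2 sets how severity changes are recorded. The general rule covers increases only: "When the severity of an AE increases over time, the increase in the severity will be recorded as a new AE". The exception is Cohort 1 of Parts A and B, and it lasts from consent until Course 1 is complete. For that period the section says that "when the severity of an AE changes over time, the decreases and increases in severity will be recorded as a new AE". The earlier record closes at that point: "the original AE will stop when the new AE starts".

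AEs that precede the first dose are in the database, because Protocol 6.2 states: "Conditions that occur after the patient has signed ICF will be recorded as AEs". When an AE ends altogether, Protocol 6.7.6.6 asks for a date and not for a new record: "If the event resolves during the study, a resolution date should be recorded".

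For counting, SAP 10.2 says that "if a patient has more than 1 AE within a PT, the patient is counted only once at the maximum severity". Tables are by dose level and route, not by cohort. SAP 10 plans no formal safety testing.

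**The concern.** TEAE occurrence is the primary safety endpoint for IM RC-P (SAP 4.2.1), so its definition should give the same answer for the same clinical course. Suppose an AE is Grade 3 three days before the first dose and falls to Grade 2 on Day 3. In Cohort 1 the fall opens a record with onset Day 3, which meets the first limb if *event* means a record. In Cohort 2 no record is opened and nothing has worsened, so there is no TEAE.

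The SAP does not mention the Cohort 1 exception and has no rule linking such records. The once-per-preferred-term rule governs how patients are counted; it does not decide which records are treatment-emergent. IM dose levels that are not selected hold Cohort 1 patients only, while the final-dose column mixes both recording rules. Dose columns could therefore differ partly because of record-keeping.

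**Working it through.** **Size inputs.** The plan gives no figure for this issue. SAP 5.3 plans 13 evaluable patients in Cohort 1 at the final IM dose and about 85 in Cohort 2; 13 + 85 = 98, which matches the stated total. The interim analysis is at 51.

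**Classification.** The two recording rules were applied to simple grade courses and the TEAE definition was then read both ways. Pre-dose AEs start on Day -5, and Course 1 is taken to end on Day 14.

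| Course of the AE | By record, Cohort 1 | By record, Cohort 2 | By episode, both cohorts |
|---|---|---|---|
| Grade 3 pre-dose, Grade 2 on Day 5 | TEAE, Grade 2 | none | none |
| Grade 4 pre-dose, Grade 3 on Day 5 | TEAE, Grade 3 | none | none |
| Grade 2 pre-dose, Grade 3 on Day 5 | TEAE | TEAE | TEAE |
| Grade 3 pre-dose, Grade 2 on Day 20 | none | none | none |
| New Grade 2 on Day 3 | TEAE | TEAE | TEAE |
| Grade 3 pre-dose, unchanged | none | none | none |

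The episode column compares the grade on treatment with the last pre-dose grade. The cohorts differ only in the first two rows, and only by record. The AE must start between consent and first dose, fall to a lower grade without resolving, and do so within Course 1. The Grade 3 or 4 tables are touched only when Grade 4 falls to Grade 3.

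**Which reading fits the sentence.** Under Protocol 6.7.6.2 every increase in severity, in every cohort, closes one record and opens another. If *event* meant a record, an increase on treatment would already be caught by its own onset date, and the second limb would add almost nothing. The limb has work to do if *event* means the episode, and on that reading the cohorts agree.

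**Size per affected patient**, if that patient has no other TEAE in the row:

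- 98 patients: 1/98 = 1.0 point
- 51 patients: 1/51 = 2.0 points
- 13 patients: 1/13 = 7.7 points
- 6 patients: 1/6 = 16.7 points

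The last case is possible because Protocol 3.1.3.3 can close a dose level at its n = 6 review. Treated but non-evaluable patients stay in the Safety Analysis Set, and the note to Protocol Figure 3 says enrollment does not pause for reviews. Actual denominators may therefore be larger and the effects smaller.

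**Range in the final-dose column.** Cohort 1 makes up 13/98 = 13.3% of it, or 13/51 = 25.5% if enrollment stops at the interim. The share of Cohort 1 patients affected is not given. Assuming 5% to 30%, the number affected is 0.05 × 13 = 0.65 to 0.30 × 13 = 3.9. The added incidence is then 0.65/98 = 0.7 to 3.9/98 = 4.0 points, or 0.65/51 = 1.3 to 3.9/51 = 7.6 points at the interim size.

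**The case for a change.** The case for a change is that the record reading is not strained. SAP 10.2 starts from AEs as entered in the case report form, speaks of one severity grade per event, and takes relationship and seriousness from questions answered for each AE. SAP Appendix I imputes onset dates AE by AE. Protocol 6.7.6.2 itself calls the lower-grade entry a new AE. A programmer following these words literally would flag it, and a short sentence saying that a record opened only for a decrease keeps the status of its predecessor would prevent that at little cost.

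Much of this stands. The text is not conclusive, *event* is undefined, and such a sentence would settle the improve-only case. It would not make the two cohorts fully comparable, though. Take Grade 3 before dosing, Grade 1 on Day 3 and Grade 3 again on Day 8. Cohort 1 has a new record on Day 8. In Cohort 2 the fall was never recorded, and Protocol 6.7.6.2 does not say whether an increase is judged against the recorded grade or the latest actual grade. If the recorded grade governs, no new record opens in Cohort 2. By record the cohorts then still differ, whatever is said about decreases. By episode, measured against the last pre-dose grade, the AE is a TEAE in neither.

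**Conclusion.** The definition leaves *event* unstated, and on one of two readings a pre-dose AE that only improves is classified differently in the two cohorts. This is a gap that analysts can be expected to fill sensibly, not an error in the analysis. The worsening limb points to the episode reading, which removes the improve-only difference. The affected pairs can also be seen: the listing of all AEs in SAP 10.2 shows onset and stop dates and severity.

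The consequences are small. The rows are descriptive, the bias is toward over-reporting, and the any-TEAE row will hardly move if most patients have some other TEAE. No decision is tied to these tables. The enrollment rules in Protocol 3.1.1 and 3.1.3.3 use named toxicities judged by the review committee, and the primary efficacy analysis does not use AE data.

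Per affected patient the effect is 1.0 point at 98, 2.0 at 51, 7.7 at 13 and 16.7 at six. Those figures assume the record reading, planned denominators and no other TEAE in the row. The number of affected patients cannot be derived from the documents. No amendment follows.

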6.7.3.1. Serum Chemistry and Hematology

Blood samples for clinical laboratory tests (serum chemistry and complete blood count [CBC], see [Table 3](#) for details) will be collected at Screening (for serum chemistry only [lipid panel and CBC are not required at Screening]), prior to the first dose in each course, and at the end of the treatment follow-up visit 30 days after the last dose of the last course of RC-P. Any Screening laboratory tests performed within 7 days of check in on Day -1 need not be repeated on Day -1.

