APPENDIX 1. SCHEDULE FOR PROCEDURES AND ASSESSMENTS**Monday Start**

Assessment ^a	Screening	Course 1 and Subsequent Courses														EOS ^h	
		1	2	3	4	5	6	7	8	9	10	11	12	13	14		
Study Day	-28 to -1	M	T	W	Th	F	Sa	Su	M	T	W	Th	F	Sa	Su	14	30 days (±3) after last dose
Weekday		M	T	W	Th	F	Sa	Su	M	T	W	Th	F	Sa	Su		M-F
Informed consent	X																
Prior Medications	X																
Demographics	X																
Medical History	X																
Height	X	X ^b															
Weight	X	X ^b															
Physical Examination ^c	X	X ^d															X
Vital Signs and Temperature ^c	X	X								X							X
Local Lab Urine Pregnancy Test (Females of Child-bearing potential)	X ^e	X ^e															X
Local Lab Serum Chemistry ^f	X ^g	X ^g															X
Local Lab Hematology (CBC) ^f		X															X

RC-P

Jazz Pharmaceuticals Ireland Limited

Protocol Amendment 02: JZP458-201

Assessment ^a	Screening	Course 1 and Subsequent Courses														EOS ^h		
		1	2	3	4	5	6	7	8	9	10	11	12	13	14			
Study Day	-28 to -1																	30 days (± 3) after last dose
Weekday		M	T	W	Th	F	Sa	Su	M	T	W	Th	F	Sa	Su			M-F
Local Lab Coagulation ^f		X																
RC-P Drug Administration (IM or IV)		X		X		X			X				X					
Pharmacokinetics		Refer to Appendix 2																
Pharmacodynamics		Refer to Appendix 2																
Immunogenicity		Refer to Appendix 2																
Adverse Event Review	X	X		X		X			X		X		X			X		X
Concomitant Medications Review	X	X		X		X			X		X		X			X		X

^a When multiple procedures are scheduled for the same time point, PK and PD samples will be taken at the protocol assigned time point as specified in Appendix 2 and other non-PK and non-PD measurements will be taken before (ie, vital signs) or after (ie, AE review, clinical laboratory evaluation) the protocol-specified PK and PD time point. The window for PK and PD assessments is specified in Appendix 2. Unless otherwise specified, all procedures are to be completed prior to dosing with RC-P.

^b Performed at the beginning of each course with a -3 day window.

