^c A complete physical examination, including a description of a review of systems, external signs of any relevant disease, and co-morbidities should be performed. Physical examinations are to be completed by a physician or other health professional licensed to perform such examinations. Findings will be documented in the patient's medical record and recorded. Blood pressure, pulse rate, and temperature should be measured after the patient has been resting for 5 minutes in a supine position; respiratory rate is not required per protocol but may be collected if it is a standard of care at the study center. Blood pressure (systolic and diastolic) and pulse rate will be measured at Screening, predose, and as per the institutional standard of care. Temperature is measured only at Screening, predose, and at EOS.

^d Physical Examination can be done within 3 days prior to each course (initial and subsequent courses).

^e If a Screening urine pregnancy test was performed within 7 days of Day 1, it need not be repeated on Day 1.

RC-P

Jazz Pharmaceuticals Ireland Limited

Protocol Amendment 02: JZP458-201

- f Clinical laboratory tests include serum chemistry (albumin, alkaline phosphatase, ALT, amylase, AST, calcium, chloride, creatinine, glucose, lipase, phosphorus, potassium, sodium, total bilirubin, direct bilirubin, total cholesterol [fasting], and triglycerides [fasting]) and CBC with differential. Lipid panel analytes are not required at Screening. Coagulation tests are to be performed at Day 1 of Course 1 and at any time the patient is symptomatic; testing will include the following: PT, aPTT, APTT activity and antigen, and Fg. See [Table 3](#) for additional information. Any laboratory parameter that is out of range and considered clinically significant (as determined by the Investigator) at the end of treatment of RC-P (last dose of the last course) must be re-evaluated until resolution. Windows for the above laboratory tests: 7 days prior to Dose 1.
- g Screening laboratory testing should be completed within 7 days of enrollment. Any Screening laboratory tests performed within 7 days of check in on Day -1 need not be repeated on Day -1.
- h For ADA positive patients, their follow-up ADA samples will be their End of Study samples ([Section 6.7.4.2.3](#) and [Appendix 2](#)).

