### 7.2. Study Day 1 and Baseline Value Definitions

#### 7.2.1. Study Day 1

Study Day 1 is defined as the date of the first dose of RC-P.

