#### 7.2.2. Baseline Value

A baseline value is defined as the latest non-missing value obtained prior to or at the start date and/or time of the first dose of RC-P.

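### The TEAE definition cuts on the calendar date of first dose, so an AE recorded with a Day 1 onset but arising before dosing counts as treatment-emergent

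*SAP*

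**What the plan says.** SAP 10.2 has two routes into the TEAE category. The first is "any event with onset date on or after Study Day 1 through the end of the study". The second is "any ongoing event that worsens in severity after Study Day 1 through the end of the study". SAP 7.2.1 fixes the anchor: "Study Day 1 is defined as the date of the first dose of RC-P". Neither clause mentions the time of the dose.

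The surrounding text matters for how this works in practice:

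- Protocol 6.2 and 6.7.6.5 start AE recording at informed consent, so AEs can exist before any RC-P is given.
- Protocol Appendix 1, footnote a, sets the default order of procedures: "Unless otherwise specified, all procedures are to be completed prior to dosing with RC-P".
- Protocol 6.7.6.2 says that an increase in severity is recorded as a new AE. For Cohort 1 (Parts A and B), from consent through the end of Course 1, a decrease is recorded as a new AE as well.
- SAP 7.2.2 treats baseline differently from AEs. It takes "the latest non-missing value obtained prior to or at the start date and/or time of the first dose of RC-P", so clock time is admitted there.
- SAP 4.2.1 makes TEAE occurrence the primary safety endpoint. SAP 10.2 tabulates TEAEs, including Grade 3 or 4 TEAEs, by dose level and route. The AE listings it describes carry onset and stop dates, with no mention of onset time.

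**The concern.** An event that starts on the morning of Day 1, before the injection or infusion, cannot have been caused by RC-P. The rule still classes it as treatment-emergent because only the date is compared. The same event dated one day earlier is left out unless it later worsens. No other passage in either document removes pre-dose Day 1 AEs.

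What is at stake is the accuracy of the TEAE tables. TEAE occurrence is a primary endpoint in a single-arm study, so no control group carries the same misclassification for comparison. The tables are also split by dose level and route, and some of those groups are small.

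**Working it through.** **Step 1. Apply the definitions to specific cases.** Inputs: the two TEAE clauses (SAP 10.2), Study Day 1 (SAP 7.2.1) and the grade-change rules (Protocol 6.7.6.2). The recorded onset is assumed to be the day on which the event or grade change occurred.

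| Case | Recorded onset | Relative to first dose | Result under SAP 10.2 |
|---|---|---|---|
| New AE on the day before dosing, no later worsening | Day -1 | Before | Not a TEAE |
| New AE on Day 1, before dosing | Day 1 | Before | TEAE |
| New AE on Day 1, after dosing | Day 1 | After | TEAE |
| Cohort 1: AE falls from Grade 4 to Grade 3 on Day 1, before dosing | New AE, Day 1 | Before | TEAE, in the Grade 3 or 4 table |
| Cohort 2: AE rises from Grade 2 to Grade 3 on Day 1, before dosing | New AE, Day 1 | Before | TEAE, in the Grade 3 or 4 table |
| Cohort 2: AE falls from Grade 4 to Grade 3 on Day 1, before dosing | No new AE | Before | Not a TEAE |

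Rows 2, 4 and 5 are the misclassified ones. Row 4 is the plainest, because an improvement seen before any drug was given becomes a Grade 3 treatment-emergent event.

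**Step 2. Look for a plan figure that depends on the rule.** There is none. The only AE-count figures are the probabilities of seeing at least one AE at 3% incidence (Protocol 8.3, SAP 5.3). From 1 - 0.97^n they are 94.9% at n = 98 (stated as 95%) and 78.8% at n = 51 (stated as 79%). Both reproduce, and neither is affected.

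**Step 3. Weight of one patient.** A patient whose only event of a given term is a pre-dose Day 1 AE adds 1/n to that row:

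- n = 98 (final IM dose, primary analysis): 1/98 = 1.0 percentage point
- n = 51 (interim analysis): 1/51 = 2.0 points
- n = 13 (one Part A Cohort 1 subcohort): 1/13 = 7.7 points
- n = 6 (minimum target in Part B Cohort 1a): 1/6 = 16.7 points

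**Step 4. Range under an assumed frequency.** The documents give no rate. Let t be the true post-dose incidence in a table row. Let q be the assumed share of patients with a pre-dose Day 1 AE in that row, independent of post-dose events. The reported incidence is t + q(1 - t).

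| True t | q = 1% | q = 5% | q = 10% |
|---|---|---|---|
| 10% | 10.9% | 14.5% | 19.0% |
| 30% | 30.7% | 33.5% | 37.0% |
| 90% | 90.1% | 90.5% | 91.0% |

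The effect shrinks as the true incidence rises, because SAP 10.2 counts a patient once per term. A summary of any TEAE at all, if near 90%, would move by at most 1 point over this range. The values of q are illustrative only.

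**The case against.** The strongest reply is that the TEAE rule applies only to AEs, and few pre-dose findings are AEs. Protocol 6.7.6.1 includes laboratory, vital-sign and examination findings when they are adverse changes from baseline that the investigator judges clinically significant. Under SAP 7.2.2 a pre-dose Day 1 value is normally the baseline itself. For CBC and lipids the schedule requires no Screening sample, and coagulation is first scheduled on Day 1 of Course 1, so no earlier value is required that could show a change. This stands as a limit on scope. It does not close the gap: the AE list in 6.7.6.1 is expressly not exhaustive, conditions arising after consent are AEs, and the Cohort 1 grade-change rule needs no new condition at all.

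A reader might go further and infer that any abnormal laboratory value in the pre-dose Day 1 sample becomes a TEAE, so that sites' choice of draw day sets the count. Appendix 1 does allow that choice ("Windows for the above laboratory tests: 7 days prior to Dose 1"). But no passage says that the sample date is the AE onset date, and an abnormal baseline value is not in itself an AE. The documents do not support that reading.

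Three further replies also have force. When procedures coincide, footnote a puts AE review after the PK/PD sample, and Day 1 IM sampling has a pre-dose and a 2.5-hour point, so the exact time of the Day 1 AE review is unclear; this does not alter a rule that looks only at the date. Treatment-related TEAEs are tabulated separately, although SAP 10.2 counts a missing relationship as related, so that safeguard is incomplete. Finally, over-counting is in keeping with other conservative rules, such as setting a completely missing onset date to the date of first dose (SAP Appendix I). A conservative default is sensible when timing is unknown, but not when the event is known to precede the dose.

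**Conclusion.** The point holds in a limited form. The date-only cut-off classes as treatment-emergent any AE recorded with a Day 1 onset that arose before the first dose. It reaches those AEs only, not abnormal baseline values in general. The clearest route is Cohort 1, which supplies about 13 of the 98 planned patients at the final IM dose, as well as the other Part A subcohorts and Part B Cohort 1. In Part A Cohort 2 only new AEs and increases in grade are affected.

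Each such patient with no later event of the same term adds about 1.0 percentage point at n = 98, and more in the smaller groups. How many there will be cannot be derived from the documents. The direction is over-counting, and no formal safety test is planned (SAP 10), so none is affected.

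A reader might also infer that the enrollment-stopping limits for allergic reaction, pancreatitis and thrombosis are affected. The documents do not say that those incidences use the TEAE flag, so this is not shown. Severity is low; the case for acting is that the correction is cheap.

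**What to change.** Reword SAP 10.2 so that both clauses share one cut-off, for example: *a TEAE is an AE with onset, or an ongoing AE that worsens, at or after the date and time of the first dose of RC-P*, leaving the end of the period as it is. This also removes the mismatch between the present clauses, the first of which includes Study Day 1 while the second starts after it.

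For AEs dated Study Day 1, classify by onset time where it is collected, and otherwise by a before/after-first-dose flag or a site query. Keep events of unknown timing as TEAEs. No true TEAE is then lost, and only events known to be pre-dose drop out.

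The cost is one SAP sentence, one field or query limited to Day 1 AEs, and minor programming and data cleaning. Dose times are already recorded (Protocol 5.9, SAP 10.1.1). The case report form was not available, so it may already collect onset time. One limit: the change does not touch post-dose improvements in Cohort 1, which Protocol 6.7.6.2 will still record as new AEs.
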